5.3.4. Supplementary Analyses

5.3.4.1. Supplementary Analysis 1 (Hypothetical Estimand)

The analysis will be performed using the Hypothetical Estimand. The treatment comparison will use the similar MMRM model as in the primary analysis. LSMs, together with the 2-sided 80% CIs for the LSMs and p-value will be calculated based on the MMRM.

5.3.4.2. Supplementary Analysis 2 (Treatment Policy Estimand)

The analysis will be performed using the Treatment Policy Estimand. The treatment comparison will use the similar MMRM model as in the primary analysis. LSMs, together with the 2-sided 80% CIs for the LSMs and p-value will be calculated based on the MMRM.

5.3.5. Sensitivity Analyses

If at least one data through Week 24 is missing and p-value is <0.2 with the primary analysis, a sensitivity analysis for primary estimand (Composite Estimand) will be performed, using multiple imputation.

Step #1: Utilize a Markov Chain Monte Carlo (MCMC) approach to impute intermediate (nonmonotone) missing data and convert the dataset into a monotone missing data pattern. One hundred monotone datasets will be imputed using the seed 12345, by treatment group.

Step #2: After imputing nonmonotone data, the remaining missing value will be imputed using the PROC MI monotone regression procedure. This approach imputes missing data in a sequential manner, for each time point, a regression model based on all available data at this timepoint (either observed or imputed) is fitted and used to impute values still missing at this timepoint. The ancillary variable included in the model will be treatment group, the stratification factors, and the mRSS scores by visit. The seed is 54321. In this way, one thousand complete datasets are generated.

Step #3: Analyze each of the 100 imputed datasets using the same model specified for the primary analysis and the results will be combined using the PROC MIANALYZE procedure.

The tipping point analysis will be implemented to assess the robustness of conclusions. A constant delta is added or subtracted to the imputed data in the direction of lack of efficacy for guselkumab and in the direction of improvement for placebo. A range of evenly spaced deltas will be used to adjust imputed values in the guselkumab and placebo group independently in order to produce a grid of delta adjustments to missing values in both groups. The size of the deltas will be chosen pragmatically, so that adjustments that lead to p-value ≥ 0.2 are encompassed in the grid. In particular, assuming MAR on placebo, ie, no delta adjustment, an adjustment on the guselkumab arm that just tips the analysis into p-value ≥ 0.2 will be included.

For each pair of delta adjustments, the point estimate of treatment effect, and corresponding p-value combined from results from 1000 adjusted datasets through the PROC MIANALYZE procedures will be presented.

Ukyo and Noma proposed the permutation-based inference methods for the analyses using MMRM that is considered to be more appropriate under small sample settings ([Ukyo 2019](#)). Their method will be applied to examine the robustness of the primary analysis result.

Step #1: Permute the treatment group indicator of the mRSS dataset. The seed is defined as 127.

Step #2: Calculate the t -statistics ($T^{(b)}(\beta_1^{null})$) for the coefficient (β_1) that indicates treatment effect by the MMRM used for the primary analysis using the mRSS dataset prepared in Step #1.

Step #3: Repeat Step #1 and #2 for B times (B=1000 in this analysis) to obtain the t -statistics. Note that the t -statistics obtained in this procedure follow the empirical null distribution estimated by the actual dataset. Therefore, statistical test and inference are considered valid even if the sample size is small and longitudinal dataset is incomplete.

The p-value will be calculated as the following equation, where $T(\beta_1)$ is the t -statistics obtained by the original mRSS dataset:

$$p = \frac{1}{B+1} \left\{ 1 + \sum_{b=1}^B I\{|T^{(b)}(\beta_1^{null})| > |T(\beta_1)|\} \right\}$$

After calculating the 10% ($T_{0.1}(\beta_1^{null})$) and 90% ($T_{0.9}(\beta_1^{null})$) quantiles of the t -statistics obtained in Step #3, the 2-sided 80% CIs for β_1 will be β where the following equation holds:

$$T_{0.1}(\beta_1^{null}) \leq \frac{\hat{\beta}_1 - \beta}{\sqrt{Var(\hat{\beta}_1)}} \leq T_{0.9}(\beta_1^{null})$$

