6.3. Measures to Minimize Bias: Randomization and Blinding

Intervention Allocation

Procedures for Randomization and Stratification

Central randomization will be implemented in this study. Participants will be randomly assigned to 1 of 2 intervention groups based on a computer-generated randomization schedule prepared before the study by or under the supervision of the sponsor. The randomization will be balanced by using randomly permuted blocks and will be stratified by presence of ILD (yes, no), baseline mRSS (low [\geq 10 to \leq 15] or high [\geq 16 to \leq 22]), and baseline anti-topoisomerase I antibody status (positive, negative). The interactive web response system (IWRS) will assign a unique intervention code, which will dictate the intervention assignment and matching study intervention kit for the participant. The requestor must use his or her own user identification and personal identification number when contacting the IWRS, and will then give the relevant participant details to uniquely identify the participant.

Blinding

To maintain the study blind, the study intervention container will have a label containing the study name, study intervention number, and reference number. A tear-off label is designed to be torn off, separated from the study intervention container, and attached to the participant's source documents. The label will not identify the study intervention in the container. However, if it is necessary for a participant's safety, the study blind may be broken and the identity of the study intervention ascertained. The study intervention number will be entered in the eCRF when the study

intervention is administered. The study interventions will be identical in appearance and will be packaged in identical containers.]

The investigator will not be provided with randomization codes. The codes will be maintained within the IWRS, which has the functionality to allow the investigator to break the blind for an individual participant.

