3. SAMPLE SIZE DETERMINATION

There is lack of positive placebo-controlled trials in dcSSc.

Taking into account the following 4 Phase 2/3 placebo-controlled trials (see [Table 2](#)) in SSc with mRSS results reported in the ClinicalTrials.gov registry, a reasonable estimate of the standard deviation (SD) to be used in the sample size calculation of this study has been taken as 8.0.

Table 2: Standard deviations of mRSS in Referenced Phase 2/3 Placebo-controlled Trials in SSc

Trial	Treatment group		Placebo group	
	N	Estimated SD	N	Estimated SD
A Double-Blind, Randomised, Placebo-controlled Trial Evaluating Efficacy and Safety of Oral Nintedanib Treatment for at Least 52 Weeks in Patients With Systemic Sclerosis Associated Interstitial Lung Disease (SSc-ILD) (NCT02597933)	288	4.582	288	4.412
A Phase 3, Multicenter, Randomized, Double-Blind, Placebo-Controlled, Parallel-Group Study to Assess the Efficacy and Safety of Tocilizumab Versus Placebo in Patients With Systemic Sclerosis (NCT02453256)	104	8.169	106	8.142
A Phase 2/3, Multicenter, Randomized, Double-blind, Placebo-controlled Study To Assess The Efficacy And Safety Of Tocilizumab Versus Placebo In Patients With Systemic Sclerosis (NCT01532869)	43	8.266	41	8.933

Trial	Treatment group		Placebo group	
	N	Estimated SD	N	Estimated SD
A Phase 2 Study to Evaluate Subcutaneous Abatacept vs. Placebo in Diffuse Cutaneous Systemic Sclerosis- a Double-blind, Placebo-controlled, Randomized Controlled Trial (NCT02161406)	44	7.562	44	7.562

[Khanna et al \(2006\)](#) revealed that a 95% confidence interval (CI) of [-4.7, -1.7] in mRSS change from baseline to 6 months was considered a clinically meaningful change. The lower bound of this 95% CI, -4.7, has been taken as the expected treatment difference in the sample size calculation of this study, assuming guselkumab can achieve a clinically meaningful change in most of guselkumab-treated participants.

Assuming an SD of 8 points, an 80% power at a 2-sided significance level of 0.20, with a 1:1 randomization ratio, to detect a treatment effect of -4.7 points, a total of at least 54 participants will be required.

Allowing for up to 2 participants randomized but without postbaseline efficacy assessments, approximately 56 (28 each) randomized participants are planned. In order to evaluate the interobserver and intraobserver variability of the mRSS to support Phase 3 planning, it is desirable for each center to randomize 3 participants at least.

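### The SAP's permutation check states no stratum restriction, although randomisation was blocked within eight strata; the consequence is small, only conservative, and confined to a sensitivity analysis

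*SAP*

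**What the plan says.** Protocol 6.3 describes the allocation: "The randomization will be balanced by using randomly permuted blocks and will be stratified by presence of ILD (yes, no), baseline mRSS" group (10 to 15, 16 to 22) and anti-topoisomerase I status. That is eight strata. The block size is not given.

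SAP 5.3.5 adds a permutation analysis to examine the robustness of the primary result, on the ground that it suits small samples better. Step #1 reads "Permute the treatment group indicator of the mRSS dataset" and fixes the seed at 127. Step #2 computes the treatment t-statistic "by the MMRM used for the primary analysis using the mRSS dataset prepared in Step #1". Step #3 repeats this ("B=1000 in this analysis") and describes the resulting test and inference as valid in small, incomplete data. The p-value and a two-sided 80% CI both come from the permuted t-statistics.

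SAP 5.3.3 defines the model. ILD and antibody status enter as additive fixed effects. The mRSS stratum is left out because baseline mRSS is a continuous covariate.

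SAP section 2 and Protocol 9.1 tie the proof-of-concept objective to p < 0.2 for the primary endpoint, and SAP 5.3.3 makes the MMRM the primary analysis. No decision rule refers to the permutation result.

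**The concern.** A permutation test takes its validity from re-drawing labels as the trial drew them. Stratified blocks keep the arms nearly balanced within each stratum. An unrestricted shuffle also produces assignments with marked within-stratum imbalance, which the schedule could not generate. The SAP's statement that the inference is valid is therefore not secured by the design.

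Model adjustment removes the main effects of ILD and antibody status and a linear baseline effect. It does not remove interactions between strata or a step at the mRSS cut-point. If these are large, the permuted t-statistics spread too widely, the p-value is too large and the 80% CI too wide.

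A second gap lies in the same sentence. The mRSS dataset is longitudinal, with assessments every 4 weeks (Protocol 1.3, Table 1), and Step #1 does not say that labels move by participant rather than by record.

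At stake is how well a supportive analysis works.

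**Working it through.** **Planned size, reproduced first.** SAP section 3 takes SD 8, power 80%, a two-sided level of 0.20 and equal arms, and its result reads "to detect a treatment effect of -4.7 points, a total of at least 54 participants will be required".

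n per arm = 2(z₀.₉ + z₀.₈)² SD² / delta² = 2(1.2816 + 0.8416)² x 64 / 22.09 = 26.1, rounded up to 27, so 54 in total. This matches. The plan randomises 56.

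**Simulation.** The documents give no operating figure for the permutation test, so it was simulated.

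- From the documents: N = 56, eight strata, delta -4.7, SD 8 (used as residual SD), nominal level 0.20, covariates as in SAP 5.3.3.
- Assumed: blocks of 2 or 4, ILD 50%, antibody-positive 40%, baseline mRSS uniform on 10 to 22, complete data, and a Week 24 ANCOVA in place of the MMRM.
- 999 permutations and 2000 trials per setting. Monte Carlo SE of a rejection rate = sqrt(0.2 x 0.8 / 2000) = 0.9 points.

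Rejection rates (%) for the adjusted statistic:

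| Stratum effects | Block | Model t-test | Free shuffle | Within stratum |
|---|---|---|---|---|
| None, no treatment effect | 2 | 21.0 | 20.7 | 20.7 |
| None, no treatment effect | 4 | 18.6 | 18.7 | 18.6 |
| Additive, 4 points each, no treatment effect | 2 | 18.6 | 18.4 | 18.6 |
| Additive, 4 points each, no treatment effect | 4 | 20.1 | 19.8 | 19.8 |
| Strong non-additive, no treatment effect | 2 | 13.0 | 13.3 | 18.7 |
| Strong non-additive, no treatment effect | 4 | 14.2 | 14.4 | 19.2 |
| None, effect -4.7 | 4 | 80.1 | 80.2 | 80.0 |
| Additive, effect -4.7 | 4 | 80.3 | 80.1 | 80.2 |
| Strong non-additive, effect -4.7 | 4 | 73.7 | 73.6 | 78.9 |

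Re-running the blocked schedule in the strong non-additive setting gave 19.2% (block 2) and 20.2% (block 4) under no effect, and 78.7% at -4.7.

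**Confidence interval.** The SAP's 80% CI scales with the permuted t quantiles. With absent or additive stratum effects and no treatment effect, the mean 80% quantile of |t| was 1.30 for both shuffles. In the strong non-additive setting it was 1.295 free against 1.121 within stratum (block 2), and 1.296 against 1.130 (block 4). The ratios 1.295/1.121 = 1.16 and 1.296/1.130 = 1.15 mean a CI about 15% wider.

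**Plausibility of that setting.** The assumed stratum means were 0, 6, -4, 8, 2, -6, 8 and -2. Weighted equally, their mean is 12/8 = 1.5 and their variance 224/8 - 1.5² = 25.75. Total SD becomes sqrt(64 + 25.75) = 9.5, above the planned 8.

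**Sensitivity to the assumed interaction.** Other simulated patterns (blocks of 4, no treatment effect) gave, free against within stratum, 18.1% v 20.8%, 13.3% v 16.6% and, in an extreme case, 10.0% v 18.9%. In the middle pattern, power at -4.7 was 76.6% v 80.4%.

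**Agreement with the primary p < 0.2.** In 1000 null trials per setting (B = 500), the free shuffle disagreed with the model p-value in 1.4% (no stratum effect), 1.7% (additive) and 1.1% (extreme interaction) of trials. Within-stratum shuffling disagreed in 1.6%, 2.2% and 8.6%.

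**Monte Carlo error of the permutation p-value at 0.2.** sqrt(0.16/1000) = 0.0126, against sqrt(0.16/10,000) = 0.004.

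**The case against.** The strongest reply is that the unrestricted shuffle does what a robustness check of the t-approximation should do. Its |t| quantile stayed near 1.30 throughout, as does the t reference on 56 - 5 = 51 degrees of freedom (1.298), so it returns the primary p-value almost exactly. The conservatism under strong interactions belongs to the additive primary model, and the restricted shuffle is the version that would part company with it. This stands.

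It also disposes of a stronger reading that a reader might draw: that the free shuffle could overturn a genuine p < 0.2 or endanger the proof-of-concept decision. It agreed with the primary verdict in about 99% of simulated trials, and no decision depends on it. Nor did any setting show inflated type I error beyond simulation error.

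Two further objections stand in part. The unrestricted shuffle is inferred from silence, and the cited method paper is not available here. But Step #1 gives a seed, and the steps that follow give the number of repetitions and a p-value formula, so a programmer would take it as complete. Also, shuffling within strata ignores blocks and only approximates the trial's scheme. It nevertheless stayed close to nominal in the main simulation, and re-running the schedule would match the design.

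**Conclusion.** The mismatch is real: Protocol 6.3 restricts allocation within strata and SAP 5.3.5 Step #1 does not. Its size is nil, within simulation error, if stratum effects are absent or additive. If they are strongly non-additive, the free shuffle rejects about 13-14% instead of 20%, loses about 4-5 points of power and widens the permutation 80% CI by about 15%. Those figures rest on assumed block sizes, prevalences and stratum means, complete data and an ANCOVA stand-in. Nothing in the documents points to interactions of that size.

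This is a minor, worthwhile clarification of a sensitivity analysis. The documents do not support calling the permutation test anti-conservative, or a threat to the primary result.

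**What to change.** Replace Step #1 with: *Permute the treatment indicator at participant level (all visits together) within each of the 8 randomisation strata (ILD x baseline mRSS group x anti-topoisomerase I status), or re-run the blocked schedule within strata.* The p-value and 80% CI formulas need no change. Settle the wording before unblinding. Optionally raise B to 10,000, which cuts the Monte Carlo SE at p = 0.2 from 0.0126 to 0.004.

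The cost is one phrase and computing time. There is one small downside: when unmodelled stratum interactions are strong, the restricted check will depart from the primary p-value more often than the free shuffle does. A sentence saying how such a difference would be read would cover this.

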5.3.6. Subgroup Analysis

Descriptive statistics of the primary efficacy endpoint will be presented by the subgroups as follows:

- Gender: Male, Female
- Age: <65 years, \geq 65 years
- Weight: \leq median, $>$ median
- Corticosteroid use at baseline: yes, no
- Presence of ILD: Yes, No
- Baseline mRSS: Low [\geq 10 to \leq 15], High [\geq 16 to \leq 22]
- Baseline anti-topoisomerase I antibody status: Positive, Negative
- Disease duration at baseline: 0-18 months, $>$ 18-36 months

5.4. Secondary Endpoints Analysis

5.4.1. Multiplicity Adjustment

No adjustments for multiple comparisons will be made across all the primary and secondary efficacy endpoints. Nominal p-values will be presented for efficacy analyses.

5.4.2. Secondary Efficacy Endpoints

The secondary efficacy endpoints are:

- Change from baseline in mRSS at Week 52
- The proportion of participants who experience worsening of mRSS at Week 24 and Week 52
- The proportion of participants achieving a score of 0.6 in American College of Rheumatology Combined Response Index in dcSSc (ACR CRISS) at Week 24 and Week 52

- Change from baseline in forced vital capacity (FVC) and percent predicted FVC at Week 24 and Week 52
- Change from baseline in the measured absolute diffusing capacity of the lung for carbon monoxide (DLCO) and the derived percent predicted DLCO at Week 24 and Week 52
- Change from baseline in digital ulcer counts at Week 24 and Week 52
- Change from baseline in Health Assessment Questionnaire-Disability Index (HAQ-DI) score at Week 24 and Week 52

5.4.2.1. Definition of Endpoints

Worsening of mRSS

An increase from baseline ≥ 5 points and $\geq 20\%$ in mRSS.

American College of Rheumatology Combined Response Index in dcSSc (ACR CRISS)

ACR CRISS is a composite response index for clinical trials in early dcSSc. Application of ACR CRISS algorithm in a randomized clinical trial is a 2-step process.

Step 1: if a patient develops any of the following conditions, they will be assigned a probability of improving equal to 0.0. Investigators will evaluate if the participants have the criterion.

- new scleroderma renal crisis
- decline in percent predicted FVC $\geq 15\%$ relative to baseline confirmed by a second FVC within one month, HRCT to confirm ILD (if previous HRCT did not show ILD) and FVC $< 80\%$ of predicted attributable to systemic sclerosis
- new onset of left ventricular failure (defined as left ventricular ejection fraction $\leq 45\%$) requiring treatment, attributable to systemic sclerosis
- new onset of pulmonary arterial hypertension on right-sided heart catheterization requiring treatment, attributable to systemic sclerosis

Step 2: for the remaining patients, compute the predicted probability of improving for each participant using the following equation (equation to derive predicted probabilities from a logistic regression model):

$$\frac{\exp [-5.54 - 0.81 * \Delta_{MRSS} + 0.21 * \Delta_{FVC\%} - 0.40 * \Delta_{Pt-glob} - 0.44 * \Delta_{MD-glob} - 3.41 * \Delta_{HAQ-DI}]}{1 + \exp [-5.54 - 0.81 * \Delta_{MRSS} + 0.21 * \Delta_{FVC\%} - 0.40 * \Delta_{Pt-glob} - 0.44 * \Delta_{MD-glob} - 3.41 * \Delta_{HAQ-DI}]}$$

where, Δ_{MRSS} indicates the change in mRSS from baseline to follow-up, $\Delta_{FVC\%}$ denotes the change in percent predicted FVC from baseline to follow-up, $\Delta_{Pt-glob}$ indicates the change in patient global assessment, $\Delta_{MD-glob}$ denotes the change in physician global assessment, and Δ_{HAQ-DI} is the change in HAQ-DI. All changes are absolute change.

Participants for which the predicted probability is greater or equal to 0.60 are considered improved while participants for which the predicted probability is below 0.60 are considered non-improved.

Forced Vital Capacity (FVC)

FVC and % predicted FVC are measurements of lung function and will be performed locally.

Diffusing Capacity of the Lung for Carbon Monoxide (DLCO)

DLCO is the measurement of lung function and will be reported locally.

% predicted DLCO (hemoglobin-corrected) is only collected at screening, while for other visits, it will be derived based on following steps:

- 1) Compute Body Surface Area (BSA) per formula as below:

$$BSA (m^2) = Weight (kg)^{0.425} \times Height (cm)^{0.725} \times 0.007184$$

The Weight of the same visit should be used, if Weight of the visit is missing then the value closest to date of DLCO measurement will be used.

- 2) Compute the predicted DLCO (ml/min/mm Hg) per formula as below:

Male:

$$\text{Predicted DLCO (ml/min/mm Hg)} = 15.5 \times BSA - 0.238 \times \text{age} + 6.8$$

Female:

$$\text{Predicted DLCO (ml/min/mm Hg)} = 15.5 \times BSA - 0.117 \times \text{age} + 0.5$$

- 3) Compute the predicted DLCO (Hgb-corrected) (ml/min/mm Hg) per formula as below:

Male:

$$\text{DLCO (ml/min/mm Hg)} \times ((10.22 + \text{Hgb}) / (1.7 \times \text{Hgb}))$$

Female:

$$\text{DLCO (ml/min/mm Hg)} \times ((9.38 + \text{Hgb}) / (1.7 \times \text{Hgb}))$$

The Hgb (g/dL) of the same visit from central lab will be used.

- 4) Compute the % predicted DLCO (Hgb-corrected) per formula as below:

$$\% \text{ predicted DLCO (Hgb corrected)} = \frac{\text{Predicted DLCO (Hgb corrected) (ml/min/mm Hg)}}{\text{Predicted DLCO (ml/min/mm Hg)}} \times 100$$

Health Assessment Questionnaire -Disability Index (HAQ-DI)

The Stanford HAQ is a brief self-report questionnaire assessing physical function pertaining to activities of daily living across 8 domains: dressing and grooming, arising, eating, walking, hygiene, reach, grip, and activities. The Stanford HAQ translated into Japanese with culturally

appropriate modifications of the arising, eating, and reach category questions will be used in the study. (Matsuda 2003).

